8.1.1. Sensitivity Analyses of the Primary Efficacy Endpoint

8.1.1.1. Complete Case Sensitivity Analysis

Should imputation of the primary endpoint be necessary, a complete case analysis will be performed in the ITT population. The complete case analysis will be exactly parallel to the planned primary efficacy analysis, except it will exclude any subjects with missing change from baseline to Visit 6 HAM-A total scores, using only observed responses. Descriptive summaries will be provided for the primary endpoint based on the complete-case data.

8.1.1.2. Control-Case Sensitivity Analysis

Should imputation of the primary endpoint be necessary, an additional sensitivity analysis will be performed assuming that subjects with missing HAM-A total scores at Visit 6 responded to treatment as if they had received placebo. Specifically, missing values for the HAM-A change from baseline to Visit 6 will be set to the mean change from baseline for the placebo group. The analysis will be otherwise parallel to that of the primary efficacy analysis with the exception that descriptive summaries will not be presented.

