	
investigational product (IP) and will be dispensed a 1-week supply of PH94B or placebo. Subjects will then commence 4 weeks of double-blind treatment with the randomized IP 4 times per day.
 
Subjects will return for weekly site visits (Visits 3, 4, and 5), in which the subject will return the IP vials dispensed at the previous visit and receive new vials. Concomitant medications and adverse events (AEs) will be recorded. During these visits, the HAM-A, Patient Global Impression of Change (PGI-C), Clinical Global Impression - Improvement (CGI-I), CGI-S, and C-SSRS will be completed. Vital signs will be collected, and nasal passages will be examined.
 
When the subject returns for Visit 6, besides the assessments completed at Visits 3 through 5, the subjects will complete the MADRS, ADN, and IADQ; and have a physical examination, ECG, laboratory tests (chemistry and blood), urinalysis, urine drug screen, and urine pregnancy test conducted. Any remaining IP vials will be collected. The subject will then come back after a 1-week washout period for the Follow-up visit (Visit 7). During this visit, AEs and concomitant medications since the last visit will be collected and the HAM-A, C-SSRS, and the 20-item Physician Withdrawal Checklist (PWC-20) will be completed.
 
For each visit following Baseline (Visit 2), a \pm 2-day window will be allowed.
 
Safety considerations:
 
Safety and tolerability of PH94B will be assessed and summarized through changes from screening in clinical laboratory values, ECGs, physical examinations, and vital sign assessments following exposure to PH94B, as well as by comparison of AEs reported during treatment with the IP. To date, limited exposure to PH94B (<2 weeks, <4 doses per day) in over 200 subjects has resulted in no serious AEs (SAEs) and no AEs occurring with statistically greater frequency for the PH94B group than for the placebo group. In addition, the PWC-20 will be administered to document any withdrawal effects that may be occurring.

PLANNED NUMBER OF SUBJECTS	Forty adult subjects will be randomized 1:1 to PH94B or placebo.

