4.1. Introduction

Data processing, tabulation of descriptive statistics, calculation of inferential statistics, and graphical representations will primarily use Statistical Analysis System Software (SAS) (release 9.4 or higher). If the use of other software is warranted, the final SAP and the statistical methodology report will detail what software was used for what purposes.

Continuous (quantitative) variable summaries will include the number of subjects (n) with non-missing values, mean, SD, median, minimum, and maximum. The minimum and maximum will be reported with the same degree of precision (i.e., the same number of decimal places) as the observed data. Measures of location (mean and median) will be reported to 1 degree of precision more than the observed data and measures of spread (SD) will be reported to 2 degrees of precision more than the observed data.

Categorical (qualitative) variable summaries will include the frequency and percentage of subjects who are in the category or each possible value. The denominator for the percentage calculation will be based upon the total number of subjects in the study population for the treatment groups unless otherwise specified. Percentages will be presented to 1 decimal place. Counts of zero will be presented without percentages.

Unless otherwise indicated, all statistical tests will be conducted at the 0.05 significance level using 2-tailed tests, and p values will be reported. Corresponding 95% confidence intervals (CIs) will be presented for statistical tests. All p values will be displayed in four decimals and rounded using standard scientific notation (e.g., 0.XXXX). If a p value less than 0.0001 occurs it will be shown in tables as < 0.0001 ; similarly, if a p value greater than 0.9999 occurs, it will be shown in tables as > 0.9999 . Confidence intervals will be reported to 1 degree of precision more than the observed data.

This study is considered a Phase 2a exploratory study under an IND application for PH94B targeting AjDA. Statistical tests will be applied and interpreted to determine feasibility and best approaches for potential Phase 2b and Phase 3 studies.

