6.1.3. Multiple Comparisons

For the primary efficacy endpoint, group differences will be assessed at $\alpha = 0.05$. No adjustments will be made for comparison of secondary or exploratory efficacy endpoints as the study is exploratory.

[figure not shown]

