treatment group. The regression model will include the following variables: baseline HAM-A total score, sex, age, LSAS total score, and analysis site. For each imputation process, a total of 25 complete datasets will be created. The random seeds to be used in the imputation process are 813616018 for the PH94B treatment group and 80521516 for the placebo treatment group.

The analysis method for the multiple imputation will match that described for the primary efficacy analysis in Section 8.1. Results from the multiply-imputed datasets will be combined using the standard Rubin's rules for multiple imputation (Little and Rubin, 1987) and will be done in SAS using PROC MIANALYZE.

Two sensitivity analyses will be performed to assess robustness of the multiple imputation results to changes in missing data assumptions. The sensitivity analyses include 1) a complete case analysis where only subjects with non-missing change from baseline in HAM-A total scores will be included, and 2) a control-case analysis, where missing change from baseline in HAM-A total scores will be imputed by the mean change from baseline for the placebo group. Sensitivity analyses are detailed in Section 8.1.1.

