8.1. Primary Efficacy Analysis

The primary endpoint will be tested for the following hypothesis:

H₁₀: Mean change in HAM-A total score from Visit 2 (Baseline) to Visit 6 does not differ between PH94B and placebo.

H₁₁: Mean change in HAM-A total score from Visit 2 (Baseline) to Visit 6 does differ between PH94B and placebo.

The estimand for the primary efficacy endpoint has the following components:

Table 4: Primary Efficacy Estimand

Attribute	Definition
Treatment	The treatment of interest is PH94B, 3.2 µg administered as an intranasal solution [REDACTED]. The active drug will be compared to a placebo control.
Population	The population of interest is adults with AjDA as defined by inclusion and exclusion criteria.
Variable of Interest	The variable of interest is change in subject reported severity of anxiety as measured by change from baseline in HAM-A total score using the SIGH-A, after 4 weeks of randomized treatment with study drug.
Intercurrent Events	Treatment discontinuation prior to the planned assessment time frame. Intercurrent events will be treated as described in Table 3.
Population Summary	The difference in change from baseline in mean HAM-A total score between PH94B-treated and placebo-treated subjects after 4 weeks of treatment.

Descriptive summaries of HAM-A total scores and change from baseline in HAM-A total scores will be provided for the primary endpoint by visit and by treatment group, based on the observed data.

An ANCOVA model with change from baseline to Visit 6 in HAM-A total scores as the outcome, treatment group as the factor, and baseline HAM-A as a covariate will be used to test the null hypothesis that there is no difference between PH94B- and placebo-treated subjects in mean change from baseline to Visit 6 in HAM-A total score. The analysis will be performed in the ITT population using SAS PROC MIXED. The following parameters will be presented: the change from baseline LS means and standard error (SE), 95% CI for the LS means, *p* value for testing if the LS mean is different than 0, LS mean difference between treatment groups (PH94B minus placebo) with SE, 95% CI for the LS mean difference, and *p* value for testing if the treatment LS means are equal.

If, for unanticipated reasons (intercurrent events), the fraction of subjects with missing change

AD-ST-33.06 Effective date: 12-Nov-2020

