10.1. Coronavirus 2019 (COVID-19) Impact

The SARS-CoV-2 virus and variants may still be a threat and safety precautions may still be in place during study enrollment. To assess the impact of the COVID-19 pandemic on study procedures, study staff will complete the COVID-19 Impact questionnaire. Should a study visit be affected by COVID-19, study staff will record how the visit was affected (missed, abbreviated, delayed, performed remotely, or otherwise deviating from the planned format in the protocol) and which procedures were impacted. All COVID-19 protocol deviations will be provided in a separate listing. This listing will include the subjects, affected visits, and affected assessments.

11. Changes from Planned Analysis

Study staff will complete the Coronavirus 2019 (COVID-19) Impact questionnaire to assess the impact of the COVID-19 pandemic on study procedures. The COVID-19 Impact questionnaire is described in Section 10.1. All COVID-19 protocol deviations will be provided in a separate listing.

The ADNMs subscales exploratory endpoints analysis will not be completed as part of this SAP.

Physical examination and urinalysis results will not be summarized using descriptive statistics but will be listed.

The treatment failure sensitivity analysis will be replaced with a control-case sensitivity analysis that imputes the mean change from baseline to Week 6 in HAM-A total scores from the placebo group for missing change from baseline responses. This approach accounts for the potential for a

high placebo response.

12. References

- ASA. (2018) Ethical Guidelines for Statistical Practice. Prepared by the Committee on Professional Ethics, April 2018. <http://www.amstat.org/about/ethicalguidelines.cfm>
- Carpenter JR and Kenward MG. *Multiple Imputation and its Application (Statistics in Practice)*. Chichester, West Sussex, UK: John Wiley & Sons; 2013.
- Graham JW, and Olchowski AE, Gilreath TD. (2007) “How Many Imputations are Really Needed? Some Practical Clarifications of Multiple Imputation Theory.” *Prev Sci.* 2007;8(3): 206-213.
- ICH (1998). ICH Harmonised Tripartite Guideline. Statistical Principles for Clinical Trials E9; 1998. https://database.ich.org/sites/default/files/E9_Guideline.pdf
- Little R and Rubin D. (1987). *Statistical Analysis with Missing Data*, New York: Wiley.
- RSS. (2014) *The Royal Statistical Society: Code of Conduct*, 2014. <https://rss.org.uk/about/policy-and-guidelines/code-of-conduct/>.

13. Tables and Listings

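### The control-case sensitivity analysis fills missing HAM-A changes with a single placebo mean and reports the ordinary ANCOVA standard error, which does not reflect the missing data when missingness is unbalanced between arms

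*SAP*

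**What the plan says.** The protocol synopsis gives the size of the trial: "Forty adult subjects will be randomized 1:1 to PH94B or placebo". SAP 4.1 states that "all statistical tests will be conducted at the 0.05 significance level using 2-tailed tests", unless otherwise indicated.

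SAP 8.1.1.2 applies whenever the primary endpoint needs imputation. It assumes that subjects without a Visit 6 HAM-A responded as placebo subjects did, and "missing values for the HAM-A change from baseline to Visit 6 will be set to the mean change from baseline for the placebo group". It then adds: "The analysis will be otherwise parallel to that of the primary efficacy analysis", except that descriptive summaries are dropped. The primary model (SAP 8.1) is an ANCOVA on the Visit 6 change in which "treatment group as the factor, and baseline HAM-A as a covariate will be used to test the null hypothesis".

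SAP 6.1.4 repeats the rule: missing changes "will be imputed by the mean change from baseline for the placebo group". SAP section 11 gives its origin: "The treatment failure sensitivity analysis will be replaced with a control-case sensitivity analysis". The analysis it replaces is the protocol's zero-change rule (Protocol Table 13-1).

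None of these places adds residual variation to the filled values, allows for uncertainty in the placebo mean, or corrects the SE. Table shell 14.2.1.3 keeps only the least-squares-means block, which in the parent shell holds the SEs, 95% intervals and p values. When more than 5% of changes are missing, the primary analysis instead uses 25 imputed datasets combined by Rubin's rules.

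**The concern.** A constant put in place of a missing value is treated by the ANCOVA as an observed patient. The effect depends on the arm.

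- **Missing on placebo.** The fill adds copies of the placebo mean. The estimate stays essentially the complete-case estimate, but the residual variance shrinks and the nominal sample size is kept, so the SE is too small.
- **Missing on PH94B.** The fill pulls the PH94B mean towards placebo, so the estimate varies less. The reported SE falls by a smaller amount, so it is too large.

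SAP 6.1.4 gives these analyses the job of testing the multiple-imputation result against other missing-data assumptions. The primary imputation assumes data missing at random. With the zero-change analysis gone, control-case is the one planned analysis of the primary endpoint that departs from that assumption. If placebo subjects are the ones lost, its p value can look stronger than the complete-case p value although it contains no more information.

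**Working it through.** **Inputs.** n = 20 per arm (Protocol synopsis); two-sided 0.05 (SAP 4.1); fill rule and model (SAP 8.1.1.2 and 8.1). The documents give no dropout rate, no split between arms and no SD in the visible text. The missing patterns below are therefore assumptions, and results are in units of the SD, σ. Also assumed: data missing completely at random, normal changes, and a placebo mean taken from the observed placebo subjects. More than 5% of 40 means at least 3 missing for multiple imputation.

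**Starting point.** With nothing missing, the simulated ANCOVA rejects 4.8-5.1% of the time, matching the nominal 5%.

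**Closed form under no treatment effect.** Let mA be missing on PH94B and mP on placebo. After the fill, the difference in means is (1 − mA/n) × (observed PH94B mean − observed placebo mean). Hence:

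- True variance = (1 − mA/n)² × [1/(n − mA) + 1/(n − mP)] × σ²
- Reported variance ≈ [(2n − mA − mP − 2)/(2n − 2)] × (2/n) × σ²
- Type I error ≈ 2 × [1 − Φ(1.96 × √(reported/true))]

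**Four missing on placebo only.** True: 1/20 + 1/16 = 0.1125. Reported: (34/38) × 0.1 = 0.0895. SE ratio √(0.0895/0.1125) = 0.89; type I error 8.1%.

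**Four missing on PH94B only.** True: 0.64 × 0.1125 = 0.072. Reported: 0.0895 again. SE ratio √(0.0895/0.072) = 1.11; type I error 2.9%.

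**Four missing in each arm.** True: 0.64 × (1/16 + 1/16) = 0.080. Reported: (30/38) × 0.1 = 0.0789. SE ratio 0.99; type I error 5.2%.

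**Simulation check** (40,000 ANCOVAs per pattern; baseline-change correlation 0, −0.3 and −0.5):

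| Missing | PH94B only: closed form (simulated) | Placebo only: closed form (simulated) |
|---|---|---|
| 2 of 20 | 3.9% (3.7-3.9%) | 6.3% (6.3-6.5%) |
| 3 of 20 | 3.4% (3.1-3.4%) | 7.1% (6.9%) |
| 4 of 20 | 2.9% (2.7-2.8%) | 8.1% (7.9-8.0%) |
| 6 of 20 | 2.0% (1.8-1.9%) | 10.3% (9.7-10.4%) |
| 8 of 20 | 1.2% (1.0-1.2%) | 13.2% (12.6-13.3%) |

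With equal numbers missing, simulated type I error was 4.8-5.0% at 2 + 2, 4.7-4.9% at 4 + 4 and 4.4-4.6% at 6 + 6. At correlation 0, the mean reported SE against the true SD of the estimate was 0.301 against 0.339 (four on placebo), 0.303 against 0.273 (four on PH94B) and 0.284 against 0.288 (four in each).

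**Random dropout with at least three missing** (correlation −0.3). Equal rates of 10-30% per arm gave 4.7-5.1%. Rates of 20% on PH94B and 10% on placebo gave 3.5%; the reverse gave 6.9%.

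**Comparator.** The complete-case ANCOVA planned in SAP 8.1.1.1 held 4.7-5.3% in every pattern.

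**The case against.** The strongest reply has four parts.

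1. **The size rests on an assumed pattern.** This stands. A reader might infer that 3-8% is a bound, or that the SE is wrong however the data go missing. Neither follows: the figures move with the amount missing, and the errors nearly cancel when the arms lose similar numbers. If four subjects were lost at random with equal rates, the chance that all four were on placebo is C(20,4)/C(40,4) = 4,845/91,390 = 5.3%. Unequal dropout would raise it.

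2. **The plan limits missing data.** This also stands. Subjects who discontinue are asked to attend an early-termination visit whose HAM-A counts as Visit 6. The value is set to missing only for loss to follow-up, inability to complete Visit 6, or use of prohibited medication. These causes could still differ by arm.

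3. **Little depends on this p value.** Largely right. SAP section 4 calls the study exploratory, no decision rule is attached to control-case, and a complete-case analysis is reported beside it. A reader might infer that the primary result is compromised or that a false positive would go unnoticed. The documents do not support that. Still, SE, interval and p value will be printed, and they should mean what they say.

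4. **The obvious repair overshoots.** Correct. Drawing missing changes from the placebo regression and combining by Rubin's rules gave 4.1%, 2.2% and 1.2% for four missing on placebo, three in each arm and four on PH94B. The planned fill gave 8.3%, 5.1% and 2.7% in the same set of runs, so the imputation is further from 5% in two of the three. With five predictors, the number in SAP 6.1.4, the ratio of reported to true SE was 1.07, 1.25 and 1.27.

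**Conclusion.** The point holds in a conditional form. The control-case SE ignores the fact that filled values are not observations, and it is miscalibrated when the arms lose different numbers. With 20 per arm, data missing completely at random and 4 of 20 missing in one arm only, type I error is about 8% (placebo) or about 3% (PH94B), with the SE about 10% too small or too large. With balanced missingness it is near 5%. The direction is fixed by the rule; the size depends on a missing-data pattern that the documents do not give. The consequence is confined to one robustness check in an exploratory trial, so priority is low to moderate.

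**What to change.** Keep the placebo-mean fill and the assumption behind it, so the point estimate is unchanged. In SAP 8.1.1.2, replace the model-based SE, interval and p value with bootstrap ones: resample subjects within each arm with their missing status, recompute the placebo mean from the observed placebo subjects, repeat the fill, refit the ANCOVA, and use the spread of the estimates. A check over five missing patterns gave type I error of 4.9-6.1% and a ratio of reported to true SE of 0.94-1.00. The SAP should fix the number of resamples, the seed and the form of the interval before unblinding; with 20 per arm, a t reference on the bootstrap SE is safer than percentile limits. Shell 14.2.1.3 needs a footnote.

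The cost is a little extra programming and a slightly liberal test in some patterns. The bootstrap SE also gets smaller as PH94B data are lost, because the fill pulls the estimate towards zero. A team that does not want that can use reference-based multiple imputation with Rubin's rules, which also removes the inflation. The SAP should then say plainly that it is conservative (type I error about 1-4%) and not describe it as only slightly less favourable.

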8.2. Secondary Efficacy Analyses

8.2.1. Analysis of Proportion of CGI-I Responders

The CGI-I secondary endpoint will be tested for the following hypothesis:

H_{20} : The proportion of CGI-I responders at Visit 6 does not differ between PH94B and placebo.

H_{21} : The proportion of CGI-I responders at Visit 6 does differ between PH94B and placebo.

The estimand for the CGI-I secondary efficacy endpoint includes the same population, treatment, and anticipated intercurrent events as the primary estimand. The variable of interest is the proportion of CGI-I responders at Visit 6. The proportion of CGI-I responders will be calculated as described in Section 6.1.7.3. The population-level summary measure is the difference in the proportion of CGI-I responders between PH94B-treated and placebo-treated subjects at Visit 6.

The PH94B and placebo proportions of CGI-I responders will be compared using a normal approximation (Wald) test for the difference between 2 binomial proportions. If expected cell sizes are less than 5, a Fisher's exact test will be used. The analysis will be performed using the ITT population. The following parameters will be presented: proportion of responders in each

treatment group, odds ratio and corresponding 95% CIs for PH49B responders versus placebo responders, and *P* value for the Wald test for equality of proportions will be presented.

Additionally, CGI-I scores and responder status will be summarized using frequencies and percentages by visit and by treatment group.

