13. STATISTICS

13.1. Statistical Analysis

This section presents a summary of the planned statistical analyses.

A statistical analysis plan (SAP) will be finalized and approved before final database lock and unblinding of the randomization code.

Unless otherwise indicated, all testing of statistical significance will be two-sided, and a difference resulting in a p value of ≤ 0.05 will be considered statistically significant.

The data will be summarized in tables, as appropriate, showing the number of subjects with non-missing data (n), mean, standard deviation, median, minimum, and maximum for continuous data and showing counts and percentage for categorical data. Data will also be listed as deemed appropriate. All statistical analyses will be performed, and data appendices will be created by using SAS. Details of the statistical approach for each endpoint will be provided in the SAP.

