13.1.4.3 Secondary Analyses

CGI-I and PGI-C at end of treatment will be analyzed using a normal approximation test for the difference between 2 binomial proportions. The null hypothesis to be tested is that there is no difference between PH94B- and placebo-treated subjects. (SAS PROC FREQ, version 9.4).

Change from baseline to Week 4 in ADNM total score will be analyzed analogously to the primary endpoint.

Change from baseline to Week 4 in IADQ total score will be analyzed analogously to the primary endpoint.

[REDACTED]

[REDACTED]

[REDACTED]

[REDACTED]

[REDACTED]

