8.2.2. Analysis of the Proportion of PGI-C Responders

The PGI-C secondary endpoint will be tested for the following hypothesis:

H₃₀: The proportion of PGI-C responders at Visit 6 does not differ between PH94B and placebo.

H₃₁: The proportion of PGI-C responders at Visit 6 does differ between PH94B and placebo.

The estimand for the PGI-C secondary efficacy endpoint includes the same population, treatment, and anticipated intercurrent events as the primary estimand. The variable of interest is the proportion of PGI-C responders at Visit 6. The proportion of PGI-C responders will be calculated as described in Section 6.1.7.4. The population-level summary measure is the difference in the proportion of PGI-C responders between PH94B-treated and placebo-treated subjects at Visit 6.

The analysis for this endpoint will be exactly parallel to the one described for the CGI-I secondary endpoint in Section 8.2.1.

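### The Wald test planned for the CGI-I and PGI-C responder comparisons has a type I error of up to 8.1% at 20 per arm, and the Fisher fallback does not prevent this

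*SAP*

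**What the plan says.** The Protocol synopsis (2.1) states "Forty adult subjects will be randomized 1:1 to PH94B or placebo", so 20 per arm. Protocol 13.1.4.3 says that CGI-I and PGI-C at end of treatment "will be analyzed using a normal approximation test for the difference between 2 binomial proportions".

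SAP 8.2.1 is more specific. The CGI-I responder proportions "will be compared using a normal approximation (Wald) test for the difference between 2 binomial proportions", and Fisher's exact test replaces it "If expected cell sizes are less than 5". SAP 8.2.2 adds for PGI-C: "The analysis for this endpoint will be exactly parallel to the one described for the CGI-I secondary endpoint in Section 8.2.1".

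On the level, SAP 4.1 has "all statistical tests will be conducted at the 0.05 significance level using 2-tailed tests", and Protocol 13.1 has "a difference resulting in a p value of ≤ 0.05 will be considered statistically significant". SAP 6.1.3 makes no multiplicity adjustment for secondary endpoints, so each p value is read at face value. SAP 6.1.7.3 and 6.1.7.4 take subjects with non-missing scores as the denominator, so fewer than 20 per arm may be analysed. Neither document writes out the variance estimator, mentions a continuity correction, or gives the test's actual size at this sample size.

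**The concern.** A Wald z test for two proportions is a large-sample method. It puts the observed proportions into the variance, and with 20 per arm this makes the standard error too small for mid-range responder rates. The test then rejects a true null more often than its nominal level. The Fisher fallback looks like protection, but it is triggered by small expected cells, that is, by rates near 0 or 1. The excess lies in the middle of the range.

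Two of the four secondary efficacy endpoints rest on this test. SAP 4 and 4.1 say the tests will be interpreted to judge feasibility and the best approaches for Phase 2b and Phase 3. A responder difference with a p value just under 0.05 would be reported as significant when a test that keeps its level would not call it so.

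**Working it through.** **Inputs.** Two-sided level 0.05 (SAP 4.1); 20 per arm (Protocol 2.1); the Wald rule with fallback (SAP 8.2.1). The documents give no responder rate for this trial, so the common null rate *p* was scanned over its whole range. The only CGI-I rates available are 75.6% and 37%, from the earlier social anxiety studies (Protocol 5.2.2).

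**Statistics.** With x₁/n₁ and x₂/n₂ responders:
- Unpooled (Wald): z = (p₁ − p₂) / √[p₁(1−p₁)/n₁ + p₂(1−p₂)/n₂]
- Pooled: z = (p₁ − p₂) / √[p̄(1−p̄)(1/n₁ + 1/n₂)]

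**Which variance the sponsor has used before.** Protocol 5.2.2 reports Z = 4.03 for 34/45 versus 17/46. The difference is 0.7556 − 0.3696 = 0.3860. The unpooled standard error is 0.0958, giving 4.03. The pooled one is 0.1041, giving 3.71. Only the unpooled form reproduces the reported figure.

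**When the fallback applies.** At 20/20 with m responders in total, the expected cells are m/2 and (40−m)/2. One of them is below 5 only if m ≤ 9 or m ≥ 31. The probability of that is 0.038 at a rate of 37% and 0.0007 at 50%.

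**Exact size.** For each of the 21 × 21 tables, apply Wald, or Fisher if the smallest expected cell is below 5, at p ≤ 0.05. Then sum the binomial probabilities of the rejecting tables under a common rate:

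| Common rate | 20% | 25% | 30% | 35% | 37% | 40% | 45% | 50% |
|---|---|---|---|---|---|---|---|---|
| Size | 3.3% | 4.5% | 5.7% | 6.7% | 7.0% | 7.5% | 7.9% | 8.1% |

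The size exceeds 5% for rates from about 27% to 73%. The maximum is 8.07% with or without the fallback.

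**Other analysed sizes, maximum over the rate.**

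| n per arm | 21/19 | 20/19 | 19/19 | 18/20 | 19/18 | 18/18 | 17/19 | 17/17 |
|---|---|---|---|---|---|---|---|---|
| Max size | 7.0% | 5.7% | 7.3% | 7.4% | 5.6% | 6.5% | 6.7% | 5.8% |

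**Worked example, 13/20 versus 7/20.** All expected cells are 10, so Wald applies. Unpooled: z = 0.30/√(2 × 0.65 × 0.35/20) = 0.30/0.1508 = 1.99, p = 0.047. Pooled: z = 0.30/√(0.25 × 0.1) = 0.30/0.1581 = 1.90, p = 0.058. Barnard p = 0.081; Fisher p = 0.113. At 20/20, seven outcomes with a six-responder gap (10 v 4 through 16 v 10) are significant under the planned rule and not under Barnard's test.

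**Alternatives.** With the same fallback, the pooled test peaks at 5.2% at 20/20 but 6.5% at 18/18. Fisher throughout peaks at 2.5% at 20/20. Barnard's test with the score statistic peaks at 5.0% (20/20), 4.6% (18/20), 4.8% (18/18) and 4.95% (17/19). Against 75.6% versus 37% at 20/20, power is 78% for the planned rule, 68% for Barnard and 58% for Fisher.

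**The case against.** The strongest reply is that the statistic is under-specified. The SAP names no variance and no continuity correction. It reports an odds ratio alongside the test, and the shell for Table 14.2.2.1 says that the p value and the odds ratio come from the same test. Read as a log-odds Wald test with the fallback, the rule peaks at 4.2% at 20/20. A continuity-corrected unpooled test peaks at 3.9%. This has some force, since the estimator needs stating in any case. But SAP 8.2.1 names a Wald test for a difference in proportions, which in ordinary use is the unpooled statistic without correction. The log-odds version still reaches 6.5% at 18/18.

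Second, 8.1% is a worst case: exactly 20 analysed per arm and a 50% rate. That is true. At 20/19 the maximum is 5.7%, at 19/18 it is 5.6%, and at rates of 25% or below at 20/20 the size is under 5%. The 37% placebo rate comes from a different disorder and an in-clinic challenge, so it is a guide and not a forecast. The Z = 4.03 check likewise describes earlier studies, and Protocol 5.2.2 attaches a Fisher label to that result. Still, every sample size examined peaks above 5%.

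Third, the trial is exploratory. Four unadjusted secondary tests already carry up to 1 − 0.95⁴ = 18.5% familywise error if independent. That limits the importance of the point. It does not justify a single test missing its own stated level.

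**Conclusion.** The concern holds. As written, the responder rule does not keep the 0.05 level set in SAP 4.1. Its exact size at 20 per arm reaches 8.1% and is above 5% for any common responder rate between about 27% and 73%. Over the other analysed sizes examined, the maximum runs from 5.6% to 7.4%. The fallback controls the error only at low or high rates.

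This rests on reading Wald as unpooled variance without continuity correction. A pooled variance does not fully cure the problem. The effect is confined to two unadjusted secondary endpoints, and the primary HAM-A analysis is untouched. It should be corrected before unblinding, but it does not threaten the trial's main conclusion.

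**What to change.** In SAP 8.2.1, and through it 8.2.2, replace the Wald/Fisher switch with one named test used whatever the cell counts: Barnard's exact unconditional test with the score statistic, two-sided at 0.05. This also removes a choice of test that depends on the data. Update the footnotes to Table 14.2.2.1 to match. SAP 4.1 promises confidence intervals corresponding to the tests, so add an interval for the difference in proportions built on the same statistic, and label the odds ratio as descriptive.

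If the sponsor prefers to keep a normal approximation, the SAP must state the variance and the continuity correction, and show the resulting exact size at the likely analysed sample sizes.

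The cost is SAP and shell wording and a change to the procedure call. The Protocol names PROC FREQ, and the statistician should confirm that the installed release offers the test. Nominal power against 75.6% versus 37% falls from 78% to 68% at 20/20, because part of the higher figure came from the inflated error rate. Barnard's test still has about 9.5 percentage points more power than Fisher at 20/20 for that alternative, and about 3 points more at 18/20.
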